## **Session C - FES Gait Assist**

Session C will consist of approximately 2 hours of periodic FES stimulation while the participant walks. The goal is to test Cionic's gait augmentation stimulation algorithms. The participant will wear sensorized leg straps equipped with FES and foot pressure sensors inside each shoe. Surface muscle stimulation will be applied gently at first, increasing slowly as directed by the participant.

### Task 1: Introduction and anatomical measurements

- Introductions to all Cionic team members and review study activities.
- Confirm signed informed consent.
- Provide opportunity for participants to change clothes if necessary.
- Measure anatomical features using a flexible tape including thigh and calf circumference and leg length.

### Task 2: Equipment setup

- Secure leg straps to the participant's body and confirm comfort.
- Initiate data collection device and ensure connection to Smartphone app.
- Record non-personally identifiable participant information within the app.
- Validate system operation by confirming communication between app and all data collection channels.
- Sensors will be calibrated by guiding the participant through specific limb movements both standing and sitting.

### Task 3: Treadmill trial

- Participant will be guided onto a treadmill with side handles.
- An overhead safety harness will be fitted to the participant.
- Walking will be initiated on the treadmill at a rate no more than the participant's comfort level at a participant-reported speed for up to 5 minutes while movement data is collected.

Data will be reviewed to confirm readiness for treadmill gait protocol.

- The process will then be repeated up to 5 times for walking intervals of up to 2 minutes while data is collected and reviewed.
- Verbal check-in with participant for pain, understanding and need for a break.

## Task 4: Treadmill trial with stimulation assist

- Participant remains on the treadmill with side handles.
- An overhead safety harness remains fitted to the participant.
- A gait assist algorithm will be entered into the Apollo system.
- Walking will be initiated on the treadmill at a rate no more than the participant's comfort level
- After notifying participant, the electrical stimulation algorithm will be applied to the leg electrodes, starting at 0mA and slowly increased until effective gait is achieved or the participant reports discomfort. If pain or discomfort is reported the stimulation and treadmill will be stopped immediately.
- The process may be repeated up to 10 times with different gait assist algorithms.
- Verbal check-in with participant for pain, understanding and need for a break.

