### AIM 3 - FES for Gait Assistance

Session C is to characterize and collect data on the impact of electrical stimulation on impacted participants' gait. This study involves placement of electrodes onto participants and delivering patterns of stimulation optimized to allow the participant to have an improved gait, as characterized by increased range of movement, speed, and self-reported assessment of their assisted walking.

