#### Statistical Analysis

This is a broad study intended to collect data on individual participants. Key measurements such as walking speed, range of motion and muscle activation may be pooled for determination of average values and deviation. This study is not intended to generate statistically significant data intended to infer any clinical diagnosis or recommendation.

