# Statistical Analysis Plan

In this analysis, we plan to investigate whether the impact of FES on gait is statistically significant relative to unstimulated gait by pairwise comparison (single sample, pre-test post-test).

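### No FES walk at a fixed setting follows tuning, and the SAP does not say which FES steps count, so choosing the FES value on the gait result is not prevented

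*Protocol*

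**What the plan says.** The SAP's opening statement is that it will "investigate whether the impact of FES on gait is statistically significant relative to unstimulated gait by pairwise comparison". Its Reported Outcomes section takes a per-person mean over steps for each condition. It does not name the algorithm, current level, attempt or step window that makes up the FES mean.

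The walking data come from Session C of the Protocol:

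- **Without FES (Task 3, treadmill trial).** One walk of up to 5 minutes, then "The process will then be repeated up to 5 times for walking intervals of up to 2 minutes while data is collected and reviewed". Nothing is adjusted toward a better gait.
- **With FES (Task 4, treadmill trial with stimulation assist).** An algorithm is loaded and current is applied "starting at 0mA and slowly increased until effective gait is achieved or the participant reports discomfort". Then: "The process may be repeated up to 10 times with different gait assist algorithms". Effective gait has no stated criterion, and no interval at a settled level is described.
- **Task 5** uses stimulation, but for exercises rather than walking.

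Aim 3 describes Session C as "delivering patterns of stimulation optimized to allow the participant to have an improved gait, as characterized by increased range of movement, speed" and self-report. The Protocol's Statistical Analysis section says: "Key measurements such as walking speed, range of motion and muscle activation may be pooled for determination of average values and deviation". The introduction to Session C adds: "The goal is to test Cionic's gait augmentation stimulation algorithms".

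**The concern.** The two sides of the paired comparison are produced differently. The noFES side is a set of timed walks. The FES side is a search: each attempt is taken upward until the gait is judged effective or discomfort is reported, and there may be up to 10 attempts. Because no walk is recorded after the search, the FES value has to come from the search itself.

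If the analyst takes the best attempt, or the one at which gait first looked effective, ordinary run-to-run variation in gait is counted as FES benefit. A paired test can then be positive when FES does nothing, and the estimate is too large when FES works. Neither the Wilcoxon alternative nor the Bonferroni correction removes a bias of this kind. If instead every step from 0 mA upward is pooled, weakly stimulated steps pull a true effect toward zero. The SAP leaves both routes open.

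**Working it through.** **1. The plan's own figure.** SAP, Power Analysis: effect size 0.7, alpha 0.05, 80% power, 18 or more participants. For a paired t-test, taken as two-sided because the SAP does not state sidedness, the noncentrality is 0.7 × √18 = 2.97 on 17 degrees of freedom. This gives power 79.9%; strictly reaching 80% needs 19. The figure of 18 is reproduced to rounding, and 18 and 0.7 serve as reference values below.

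**2. Model with no FES effect.** For participant i the difference is

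D_i = b_i + F_i − C_i

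- b_i is between-person variation in the difference, with SD τ.
- C_i is the mean of 6 noFES runs (1 + 5, from Task 3).
- F_i is built from up to 10 FES runs (Task 4) with independent run-to-run SD σ.
- The run-noise share is ρ = σ²/(σ² + τ²).
- A run looks effective when the gait judgement exceeds +1 SD. The judgement has correlation r with the metric.
- The test is t = mean(D)/(SD(D)/√18), rejecting at two-sided p < 0.0125 (SAP, Tests of Statistical Significance).

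σ, τ, r and the +1 SD threshold are assumptions, because the documents give no SD. Two settings bracket the main result:

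- High: σ = 1 and τ = 0.5, so ρ = 1/(1 + 0.25) = 0.8, with r = 1.
- Low: ρ = 0.2 with r = 0.5.

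**3. Rejection rate with up to 10 attempts (nominal 1.25%).**

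| How the FES value is formed | Low | High |
|---|---|---|
| All 10 runs always performed and averaged | about 1.0–1.3% | about 1.0–1.3% |
| Average up to the first effective-looking run | 1.5% | 9.5% |
| First effective-looking run only | 7% | 93% |
| Best run | 12% | 100% |

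With a still smaller noise share (ρ = 0.1, r = 0.5) the three selective rules give 1.3%, 4.0% and 5.9%. A separate run at a setting fixed beforehand gives 1.1–1.4%.

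**4. Size of the spurious effect for the best of 10.** With r = 1 the mean bias is 1.54 run SDs (1.16 for the best of 5). Scaling total variance to 1, so that σ = √ρ:

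| ρ | Bias 1.54 × √ρ | Standardized effect | Rejection |
|---|---|---|---|
| 0.10 | 0.49 | 0.50 | 29% |
| 0.25 | 0.77 | 0.82 | 74% |
| 0.50 | 1.09 | 1.25 | 99% |
| 0.75 | 1.33 | 1.68 | 100% |

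From ρ = 0.25 upward the artefact exceeds the effect of 0.7 that the study was sized for.

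**5. Stopping within an attempt.** Take each attempt as a ramp of 8 levels (assumed), stopped at the first level above +1 SD, with 10 attempts and ρ = 0.10, 0.25, 0.50:

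- All ramp steps pooled over all attempts: 1.1–1.3%, bias about 0.
- Each attempt averaged first, then attempts weighted equally: 1.9%, 2.8%, 7.6%.
- Only the final level of each attempt: 13%, 41%, 87%.

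**6. Dilution.** Suppose, for illustration only, that a true effect rises linearly from zero at 0 mA to Δ at the final level, with equal time at each level. The pooled ramp mean then estimates Δ/2, not Δ.

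**The case against.** A reader might infer that the FES side is selected on the outcome and that the bias always inflates the effect. The documents do not support that stronger reading, for five reasons:

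- **No selection rule is written.** Reported Outcomes averages over steps and names no best, final or first-effective run. Read literally, all FES steps count. Steps 3 and 5 then give a nominal error rate, and the likelier fault is dilution.
- **Stopping across algorithms is assumed.** In Task 4, reaching effective gait ends one ramp. The text on repeats does not say that attempts stop once one succeeds, and testing several algorithms is the stated goal of the session.
- **The overlap of tuning target and outcome is likely, not certain.** Effective gait is undefined and the SAP does not name its four metrics. Aim 3 and the Protocol's Statistical Analysis section both point to speed and range of movement, which makes overlap probable. The Protocol does not say that the judgement is visual.
- **The largest figures need noisy, independent runs and a judgement that tracks the metric perfectly.** Means over many treadmill steps may be much less noisy.
- **Tuned FES against no FES is a legitimate comparison.** Individual tuning is part of the intervention, so tuning on one side only is not in itself a bias.

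All of this stands and limits the claim. What it does not supply is a rule. Task 4 permits but does not require further attempts, so running all of them is not guaranteed. Taking the best or last setting would be a natural choice in a session meant to test algorithms, and the SAP does not exclude it. The Protocol's remark that the study is not aimed at statistical significance does not help either, because the SAP does plan significance tests.

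**Conclusion.** The concern holds in this form: the only FES walking described is tuning walking, no FES walk at a fixed setting exists to be analysed, and the SAP does not define the FES mean. Outcome-based selection is therefore not prevented, though it is not prescribed. The consequence runs from nil to a near-certain false positive, depending on an unstated rule together with an unknown run SD and judgement-metric link. Under each selective rule examined the bias is upward; under full pooling of ramp steps a true effect is diluted. The percentages show sensitivity to the missing rule and do not predict this study's error rate. The absence of a fixed-setting FES walk follows directly from the text and needs none of these assumptions.

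**What to change.** Separate tuning from evaluation.

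- **Protocol, Task 4.** After tuning ends, add one short recorded FES interval with the algorithm and setting fixed beforehand. Match its length to a Task 3 interval (up to 2 minutes) and keep it whatever the gait looks like.
- **SAP, Reported Outcomes.** Compute the FES value only from that interval, against a pre-specified matching Task 3 interval. Describe all tuning runs as development data outside the test. State how a participant without an evaluation interval is handled.
- **Reconcile the amendment with existing text.** Task 4 allows repeats only with different algorithms, so walking again with the same one is not already covered. It also requires stimulation and treadmill to stop on pain or discomfort. The titration and stopping rules stay with the investigator; the new wording must be consistent with them and should not set what follows such a stop.
- **If no such walk can be added.** Fix in the SAP, before analysis, which FES run and steps count, by a rule that does not depend on the gait result, and describe the estimate as coming from tuning data. This is weaker, because a step window cannot fully undo the effect of attempts that ended on good gait.

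The cost is a short amendment and a few SAP sentences, a slightly longer session or one fewer algorithm tried, and fewer FES steps per person in the test.

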## Task 5: Stimulated Assisted Exercise

- The participant will choose 1-3 exercises that they already do regularly as part of their physical therapy. If none are identified, seated toe raises, half raises, and leg extensions will be suggested
- Participant will complete 1-10 reps of each to calibrate the Apollo device
- Participant will repeat this process with low stimulation turned on
- Based on participant feedback, stimulation parameters will be tuned as much as needed to maximize comfort and utility

After completion of all tasks, equipment will be removed from the participant and sanitized with isopropyl alcohol. A brief post-study survey will be administered verbally or via computer by the study coordinator.

## Pediatric Accommodations

All sessions were designed to accommodate children by aiming for a total time of < 1.5 hours. In addition, entertainment activities like books, coloring pens and paper, and an ipad with childrens games will be available for children to play during setup times (as long as parents approve). Children will also be addressed directly to ensure they fully

comprehend their study rights and to confirm that they are in full control of their participation.

## Risk & Benefit Assessment

The Apollo System represents minimal risk to the participants participating in each session of the data collection study. Like with any study of this kind, there are some known risks, that although rare, are associated with participation:

- Some participants may experience slight pain or discomfort from the electrical stimulation
- Minor skin irritation at the site of sensor/electrode placement
- Some participants may experience anxiety or anxiousness due to the anticipation of receiving an electrical stimulation
- Injury caused by unintended falls
- Exposure to COVID-19 or other communicable disease

It is not always possible to know all of the risks associated with a study like this one. If any new risks are reported for this study, someone from the study team will let the participant know so that they can decide if they would like to continue taking part.

## Risk Mitigation Strategies

Cionic has done the following things to reduce the risks to participants.

- Have done internal experiments and made design modifications to increase safety
- Cionic team is well trained and to strictly follow the study protocols
- Participants will have the option to wear a safety harness secured overhead to protect them from falls. Session C will require all participants to be in harness.
- The testing area will be safe, well lit and clear of all obstacles
- Any actions will be discussed with the participant prior and their comfort will be monitored throughout the study
- Participants will self manage a walking speed and control their level of electrical stimulation for their own comfort level
- A COVID safety protocol will be strictly adhered to, requiring all people who visit the site to check temperatures, practice social distancing, require mask

wearing and follow all other CDC guidelines to prevent the spread of COVID-19

## **Benefits**

This study is intended to benefit future participants, should it prove to provide great knowledge to clinicians and therapists of possible targeted treatments for neurological injuries or conditions that impact the lower extremities and limit mobility.

## **Participant Identification, Recruitment & Informed Consent**

### Method

Cionic will be working directly with physical therapy providers and participant advocacy groups to identify an impacted population. Starfish Therapies will identify existing physical therapy patients and will refer them by email to Cionic. In addition, Cionic will be utilizing the services of a third-party recruiter, User Interviews, to recruit participants in the adult study. User Interviews will serve as our primary recruiting tool for adults, but may also contribute toward pediatrics as well. User Interviews is an online platform that will email our recruitment flyer to individuals who have registered with the site expressing desire to participate in research. Interested candidates will complete the short screener survey.

The PI will reach out candidates who qualify for the study to set up a Zoom meeting to introduce candidates to the study and further screen participation based on the candidate's ability to walk safely and grasp basic compression. All the discussion and dialogue will follow a script. There will also be a short slide deck that will be shared with all potential participants that shares information about Cionic and the study.

Candidates that qualify and are interested in participating will be sent the digital Informed Consent form and virtually walked through it. Candidates do not need to sign the consent prior to arriving for data collection. After the Zoom meeting, candidates who qualify will be notified to schedule a time slot to participate using Google calendar. When they arrive, the Consent doc will be reviewed and signed if it has not already been done. After the data collection is completed, User Interviews disburses the Amazon gift card compensation to participants digitally.

We will also post recruitment pages on our website (one for pediatrics and one for adults). Interested candidates who click through the website or email [[contact]](mailto:[contact]) will be contacted via email to begin the same screening process outlined above.

Physical copies of the recruitment flyer may also be posted at local physical therapy clinics if they agree to allow us to post them. The screening and intake process will be identical to what is identified above.

### Consent Process

Selected participants, and/or parents of pediatric participants, will be provided an PDF electronic consent form for their review. A member of the Cionic team will walk the participant through the informed consent form and encourage them to take time to review and reach out with any questions at all. The participants will be sent a DocuSign link to provide consent signature. Alternatively, they can bring the signed paper informed consent form to their first visit. In addition, basic assent forms will be shared with pediatric participants. All forms will be stored on a secure server, paper forms will be digitized and destroyed.

### Participant Capacity and Comprehension

The study's inclusion criteria and recruitment plan may include individuals with impairments that are sometimes associated with decision making impairments and/or language impairments. The pre-screening video conference call is in place to determine if the severity of these impairments will require additional safeguards or if the interested party will need to be excluded from the study.

### Study Withdrawal

During the consent process participants will be informed that they may withdraw from the study at any time. We will confirm that they understand that they have this option. Participants will be entitled to financial compensation if they withdraw from the study for each session that they physically attend. Participants will not be compensated for data collection sessions that they cancel or miss.

## **Data Storage, Monitoring and HIPAA**

This study involves the collection of data from sensors on the Apollo system as well as possible external kinematic data collection systems for validation. No data collected includes personally identifiable information. The devices comprising the system connect wirelessly via Bluetooth to an application running on a smartphone.

The smartphone's camera will also record video of the lower body only. The participant's face and voice will not be recorded. The content of the data will be uploaded to a secure server. Each set of data will be organized using a unique numerical identifier that does not include PHI (e.g., initials) such as date of testing and study Session. This unique identifier will be recorded separately in a participant tracking file which will include demographic data such as gender and age, diagnosis, time since onset and qualitative rating of their mobility. Adverse events and protocol deviations will be recorded for each participant. This data will also be stored on a secure server.

Primary Investigator [name] will be responsible for ensuring participants' safety on a daily basis. Data collected from this study will be reviewed on a weekly basis by the PI and Sponsor for each week there are study participants. All data collected on paper and entered into electronic format will be verified by a second individual and discrepancies will be reviewed by the PI for resolution. Resolution can include correction of the entry, leaving the entered data in place, or removal of the specific data. There is no DSMB for this study.

All Adverse Events (AEs) will be reviewed by the PI within one business day of occurrence. AEs determined to be Serious Adverse Events related to subject safety will be reported to Ethical & Independent Review Services IRB within one business day of review by the PI. Adverse Events and Unanticipated Problems will be reviewed on a monthly basis in order to ensure good practice and identify any emerging issues of concern. The PI will determine whether the study should be modified based on these findings.

Quality assurance activities include following written and consistent procedures. Data collection pages will be reviewed monthly to ensure the quality of the data collection, management and analysis

The study sponsors recognize the requirement to adhere to the Health Insurance Portability and Accountability Act (HIPAA). As stated, we will not be recording PHI and data will be stored on a secure server. Additionally, individual data will not be publicly disclosed. In the future, aggregate data from the study (mean, variance, demographic data) may be disclosed to the FDA to support regulatory submissions.

#### Data Storage and Contact for Future Studies

In the screening questionnaire and Informed Consent doc, participants will indicate whether they would like their information to be saved for future studies. If they select “Yes”, their information will be saved. If they select “No,” their information will be destroyed from all databases.

#### Statistical Analysis

This is a broad study intended to collect data on individual participants. Key measurements such as walking speed, range of motion and muscle activation may be pooled for determination of average values and deviation. This study is not intended to generate statistically significant data intended to infer any clinical diagnosis or recommendation.

#### Debriefing Procedures

After each session of the study there will be a post-study debriefing with the participant where they will be encouraged to give feedback and complete the Exit Interview.

